## 5.1.1 General Study Level Definitions

### 5.1.1.1 Study and Period Day

Study day for an event or measurement occurring before the date of the first dose of Treatment Period 1 will be calculated as follows:

Study Day=Event/Measurement Date–Date of First Dose

Study day for an event or measurement occurring on the date of the first dose of Treatment Period 1 is 1. Study day for an event or measurement occurring on or after the date of the first dose to the date of the last dose including Run-Out period will be calculated as follows:

Study Day = (Event/Measurement Date–Date of First Dose) + 1

For events or measurements occurring after the date of the last dose including Run-Out period study day will be prefixed with ‘+’ in the data listings and will be calculated as follows:

Study Day = + (Event/Measurement Date–Date of Last Dose of the study)

Period day for an event or measurement occurring on the date of the first dose in a Treatment Period is 1. Period day for an event or measurement occurring on or after the date of the first dose to the day before the date of the first dose in the following Treatment Period will be calculated as follows:

Period Day = (Event/Measurement Date–Date of First Dose in a Treatment Period) + 1

There is no Study Day 0. For the purpose of the study participant data listings, study day or period day will not be calculated if the event/measurement date is partial. Instead, study day or period day will be presented as ‘--’ in the relevant participant data listing. [Table 5-1](#) below describe the ranges of study and period days during the study.

**Table 5-1: Study days and periods**

	Screening & Run-In	Treatment Period 1	Treatment Period 2	Run-Out Period	Safety FU Period
	Day-42 to Day -1	Day 1 to Day 84	Day 85 to Day 168	Day 169 to Day 182	Day 183 to Day 218
Study Day	-42 to -1	1 to 84	85-168	169-182	+1 to +35
Period Day		1 to 84	1 to 84		

### 5.1.1.2 Study Periods

The maximum study duration per study participant will be 37 weeks.

- Screening Period (Day -42 to Day -15): Eligibility will be assessed during the Screening Period of up to 28 days
- Run-In Period (Day -14 to Day -1): Study participants who have been confirmed eligible to participate in the study will be randomized 1:1:1 to study treatment. During the 2-week Run-In Period, all study participants will receive placebo sc QW and will be blinded to this treatment.

---

- Treatment Period 1 (Day 1 to Day 84): Study participants will receive their randomized treatments for the first 12-week Treatment Period.
- Treatment Period 2 (Day 85 to Day 168): Study participants will receive their randomized treatments for the second 12-week Treatment Period.
- Run-Out Period (Day 169 to Day 182): At the end of both 12-week Treatment Periods, all study participants will receive placebo sc QW during a 2-week Run-Out Period and will be blinded to this treatment.
- Safety Follow-up Period (SFU, Day 183 to Day 218): Study participants who complete both Treatment Periods and Run-Out Period will enter the 5-week SFU Period.
- Study participants who permanently discontinue IMP are encouraged to complete the EOT/EW Visit and the SFU/End of Study (EOS) Visit. In these cases, the SFU will not take place between study Day 183 to Day 218.
- Safety analysis will include periods from Run-In through end of SFU period. Efficacy, PK and PD analysis will include data collected from Treatment Period 1 to end of SFU Period.

Efficacy, PK and PD measurements collected post-Baseline and up to and including Visit 15 will be allocated to Treatment Period 1. Efficacy, PK and PD measurements collected after Visit 15 and up to and including Visit 27 will be allocated to Treatment Period 2.

For the purposes of analysis, data including AEs, IPDs, and medications will be assigned a study period using the rules summarized in Appendix 4 [Section 8.4](#).

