IMP discontinuation/study withdrawal criteria	X	X	X	X	X	X	X	X	X	X	X	X	X	X	X	
Adverse event review	X	X	X	X	X	X	X	X	X	X	X	X	X	X	X	X

Table 1-2: Schedule of Activities (Period 2 through End of Study)

Procedure	12-week Treatment Period: 2												Run-out	Run-out	EOT/EW	SFU/EOS
Visit number	15	16	17	18	19	20	21	22	23	24	25	26	27	28	-	-
Visit window	±2d	±2d	±2d	±2d	±2d	±2d	±2d	±2d	±2d	±2d	±2d	±2d	±2d	±2d	±7d	±7d
Week	13	14	15	16	17	18	19	20	21	22	23	24	25	26	28	32
Day	85	92	99	106	113	120	127	134	141	148	155	162	169	176	190	218
Concomitant medication review	X	X	X	X	X	X	X	X	X	X	X	X	X	X	X	X
IMP administration	X	X	X	X	X	X	X	X	X	X	X	X	X(pb)	X(pb)		
PK ^h	X	X							X				X			
ADA ^h	X	X							X				X		X	X
IgG (total, subclasses) ^h	X	X			X				X				X		X	X
IgG binding, in vitro assay ^{h,i}	X												X			X
Blood sampling for DNA and RNA analysis															X	
Exploratory biomarkers	X ^{f,g}												X ^{f,g}			X ^g

ADA=anti-rozanolixizumab antibodies; BPI-SF=brief pain inventory-short form; C-SSRS=Columbia Suicidality Severity Rating Scale; d=day; EOS=End of Study; EOT=End of Treatment; EW=Early Withdrawal; FIIQR=Revised Fibromyalgia Impact Questionnaire; Ig=immunoglobulin; IGRA=interferon gamma release assay; IMP=investigational medicinal product; NRS=numeric rating scale; pb=placebo; PK=pharmacokinetics; SFU=Safety Follow-up; TB=tuberculosis

Note: Assessments in the weekly columns are meant to be performed at the start of that Week prior to dosing, unless otherwise specified.

Note: The BPI-SF should be completed by the study participants in a quiet place prior to other patient-reported outcomes or protocol-specified assessments at each visit.

^a A full C-SSRS assessment will be performed only when the study participant has a positive response to the suicidal ideation query. If a study participant has active suicidal ideation as confirmed by the answer 'Yes' to Question 4 or Question 5 of the C-SSRS assessments, the study participant will be excluded or withdrawn from the study and immediately referred to a mental healthcare professional. A C-SSRS assessment may be conducted at other visits at the discretion of the investigator.

^b Vital signs comprise systolic and diastolic BP, pulse rate, and temperature. At Visit 15 and Visit 16, vital signs will be measured prior to IMP administration, at the end of the infusion (+5 min) and at 2 hours after the end of infusion (±15 min). At Visit 17, 18, and 19, vital signs will be measured prior to IMP

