**Table 5-2: Definition of Baseline**

Endpoint	Definition of Baseline
Hematology, serum chemistry, urinalysis, vital signs	Baseline is defined as the most recent value obtained prior to the first dose of IMP in the Run-In Period, or Screening if this is missing.
Efficacy	
Baseline is defined as the measurements on Day 1 (Visit 3, Week 1) prior to administration of treatment or during Run-In Period depending on the endpoint:
 
 
For BPI-SF, the Baseline measurement is at Day 1 (Visit 3, Week 1). If Day 1 measurement is missing, then the Screening measurement will be used.
 
For Pain NRS, and Fatigue NRS, the Baseline measurement will be the average of the 7 days prior to Day 1 (Visit 3, Week 1), not including Day 1 data. If there are <3 assessments available within the 7 days, the Baseline measurement will be missing.
 
For FIQR, the Baseline will be the last assessment before Day 1. This is Day -7 (Visit 2, Week -1) or Screening visit if Day-7 is missing.
 
 
Note that for all endpoints listed above, if a dose of study medication was not received at Visit 3, but the efficacy assessment was performed at Visit 3 (or Visit 2 for FIQR), the Baseline assessment would be defined as above.

Pharmacodynamics (PD)	
Baseline is defined as the latest non-missing assessment performed prior to dosing on Day 1 (Visit 3, Week 1). If Day 1 measurement is missing, the Run-In (Visit 1, Week -2) measurement will be used.
 
Note that if a dose of study medication was not received at Visit 3, but the PD assessment was performed at Visit 3, this would still be used as the Baseline assessment.

Pressure Pain Threshold	
Baseline is defined as the average of the three assessments performed per site, prior to dosing on Day 1 (Visit 3, Week 1).
 
Note that if a dose of study medication was not received at Visit 3, but the Pressure Pain Threshold assessment was performed at Visit 3, this assessment would still be used as the Baseline assessment.

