**Table 5-5: Period descriptions**

Periods	Full Description	Data Display Description
	Pre-Screening	Pre-Screening
0	Screening (Day -42 to Day -15)	Screening
1	Run-In (Day -14 to Day -1)	Run-In
2	Treatment Period 1 (Day 1 to Day 84)	TP1
3	Treatment Period 2 (Day 85 to Day 168)	TP2
4	Run-Out (Day 169 to Day 182)	Run-Out
5	Safety follow-up (Day 183 to Day 218, note that if a participant withdraws prior to this point SFU will not take place between Day 183 and 218)	SFU

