#### **5.6.9.5 Potential Drug-Induced Liver Injury (pDILI)**

The number and percentage of participants who meet one or more of the following pDILI criteria at any visit (including unscheduled visits) will be summarized by treatment period and treatment group, based on the SS-r:

- Participants with at least one post-Baseline liver laboratory assessment
- Incidence of potential hepatotoxicity with symptoms potentially associated with hepatitis or hypersensitivity
- Incidence of potential hepatotoxicity with no symptoms potentially associated with hepatitis or hypersensitivity
- Laboratory criteria for pDILI:
  - (AST or ALT  $\geq 3 \times$  ULN) and TBL  $\geq 1.5 \times$  ULN
  - (AST or ALT  $\geq 3 \times$  ULN) and TBL  $\geq 2 \times$  ULN
  - (AST or ALT  $\geq 3 \times$  ULN) and TBL  $\geq 2 \times$  ULN and ALP  $< 2 \times$  ULN (Hy's Law)

In order to meet the above criteria, a study participant must experience the elevation in bilirubin and ALT or AST (and the absence of the ALP elevation) at the same visit. For example, a study participant who experiences a  $\geq 2 \times$  ULN elevation of bilirubin at one visit and a  $\geq 3 \times$  ULN elevation in ALT (or AST) at a subsequent visit has not fulfilled the Hy's law criteria. If participant meets part of one criterion but at least one parameter is unknown, then he/she should not be considered for meeting the criterion.

Additional analyses for liver function tests (LFTs) will be performed to assess the potential for liver toxicities in accordance with the United States Food and Drug Administration guidelines. Per guidelines, the following criteria will be used to define levels of LFT elevation:

- Aspartate aminotransferase (AST):  $> 3 \times$  ULN,  $> 5 \times$  ULN,  $> 8 \times$  ULN,  $> 10 \times$  ULN,  $> 20 \times$  ULN
- Alanine aminotransferase (ALT):  $> 3 \times$  ULN,  $> 5 \times$  ULN,  $> 8 \times$  ULN,  $> 10 \times$  ULN,  $> 20 \times$  ULN
- AST or ALT:  $> 3 \times$  ULN,  $> 5 \times$  ULN,  $> 8 \times$  ULN,  $> 10 \times$  ULN,  $> 20 \times$  ULN
- Total bilirubin (TBL):  $> 1.5 \times$  ULN,  $> 2 \times$  ULN
- Alkaline phosphatase (ALP):  $> 1.5 \times$  ULN

The number and percentage of study participants who meet one or more of the above LFT elevation criteria at any visit (including unscheduled visits) will be summarized by treatment period and treatment group, based on the SS-r.

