## 8.4 Appendix 4: Period of Onset Assignment

### 8.4.1 Adverse Events and IPDs

The period of onset for AEs and IPDs is determined in the following way:

- If the event occurs prior to the date of first dose of IMP in Run-In, then the event is assigned to the Screening Period.
- Events are assigned to the Run-In Period in the following cases:
  - If the event occurs on or after the date of first dose of IMP in Run-In and prior to the date of first dose of IMP in Treatment Period 1.
  - If the study participant withdraws during Run-In (ie prior to the first dose of IMP in Treatment Period 1) and the event occurs on or after the date of first dose of IMP in Run-In and within 6 days after the date of last dose of IMP prior to withdrawal.

- Events are assigned to Treatment Period 1 in the following cases:
  - If the event occurs on or after the date of first dose of IMP in Treatment Period 1 and prior to the date of first dose of IMP in Treatment Period 2.
  - If the study participant withdraws during Treatment Period 1 (ie prior to the first dose of IMP in Treatment Period 2) and the event occurs on or after the date of first dose of IMP in Treatment Period 1 and within 6 days after the date of last dose of IMP prior to withdrawal.
- Events are assigned to Treatment Period 2 in the following cases:
  - If the event occurs on or after the date of first dose of IMP in Treatment Period 2 and prior to the date of first dose of IMP in Run-Out.
  - If the study participant withdraws during Treatment Period 2 (ie prior to the first dose of IMP in Run-Out) and the event occurs on or after the date of first dose of IMP in Treatment Period 2 and within 6 days after the date of last dose of IMP prior to withdrawal.
- Events are assigned to the Run-Out Period in the following cases:
  - If the event occurs on or after the date of first dose of IMP in Run-Out and within 6 days after the date of last dose of IMP in Run-Out.
- Events are assigned to the SFU in the following case:
  - If the event occurs on or after 7 days after the date of last dose of IMP.

For AEs, the above rules are applied after any date imputation.

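### SAP 5.1.1.2 gives safety laboratory data no period rule for pre-dose samples, so its general definitions would count some liver elevations seen before any rozanolixizumab dose as rozanolixizumab

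*SAP*

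**What the plan says.** SAP 5.1.1.2 contains two visit-based rules. The first is "Efficacy, PK and PD measurements collected post-Baseline and up to and including Visit 15 will be allocated to Treatment Period 1". The second is "Efficacy, PK and PD measurements collected after Visit 15 and up to and including Visit 27 will be allocated to Treatment Period 2". Both assign the sample taken at the opening visit of a period to the period just finished. Neither names haematology, chemistry or liver tests.

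For other data the same section says that "data including AEs, IPDs, and medications will be assigned a study period using the rules summarized in Appendix 4". Appendix 4 works by date, and its Treatment Period 2 rule begins "If the event occurs on or after the date of first dose of IMP in Treatment Period 2". It does not separate before from after dosing on that date, and it has rules only for adverse events, protocol deviations and medications.

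The general definitions point the same way. SAP 5.1.1.1 makes a measurement on the date of a period's first dose Period Day 1. Table 5-5 gives day ranges such as "Treatment Period 2 (Day 85 to Day 168", with Treatment Period 1 on Days 1 to 84 and Run-Out on Days 169 to 182.

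The protocol schedule places laboratory tests at Visits 3, 7, 11, 15, 19, 23 and 27 after the start of the Run-In and before EOT, and notes: "Assessments in the weekly columns are meant to be performed at the start of that Week prior to dosing, unless otherwise specified". For laboratory data, SAP Table 5-2 states that "Baseline is defined as the most recent value obtained prior to the first dose of IMP in the Run-In Period", so the Visit 3 sample is post-Baseline. SAP 5.6.9.5 counts participants who meet a liver criterion "at any visit (including unscheduled visits) will be summarized by treatment period and treatment group, based on the SS-r".

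**The concern.** A sample drawn before the first dose of a period reflects the treatment of the previous period. The SAP accepts this for efficacy, PK and PD. In 5.7 it also ends the 12-week ADA exposure window of Sequence 1 at Visit 15 and starts the ADA Baseline of Sequence 2 there. If the general definitions are followed for laboratory data, IgG and liver chemistry taken at the same Visit 15 would fall in different periods, and the SAP gives no reason.

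In 5.6.9.5 the period decides the treatment column, because Table 5-3 defines treatment groups by sequence and period. An any-visit count shows no visit, so the table itself gives the reader no way to correct the column. Protocol 9.4.1 wants safety events shown with the treatment at the time they occurred. At stake is the between-treatment reading of the liver-safety tables.

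**Working it through.** No power or alpha figure is involved. The check maps visits to periods.

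**Inputs.** Laboratory visits: Protocol Tables 1-1 and 1-2. Period limits: SAP Tables 5-1 and 5-5. Treatment groups: SAP Table 5-3. Planned size: 20 per sequence, Protocol 4.1.

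**Visit days.** Day = 1 + 7 × (visit − 3). This gives Day 1 for Visit 3, Day 85 for Visit 15 and Day 169 for Visit 27, matching SAP Tables 5-2 and 5-8.

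**Allocation of each scheduled sample.**

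| Visit | Day | Doses received before the sample | Period by day range | Period by doses received |
|---|---|---|---|---|
| 3 | 1 | 2 in Run-In | Period 1 | Run-In |
| 7 | 29 | 4 in Period 1 | Period 1 | Period 1 |
| 11 | 57 | 8 in Period 1 | Period 1 | Period 1 |
| 15 | 85 | 12 in Period 1 | Period 2 | Period 1 |
| 19 | 113 | 4 in Period 2 | Period 2 | Period 2 |
| 23 | 141 | 8 in Period 2 | Period 2 | Period 2 |
| 27 | 169 | 12 in Period 2 | Run-Out | Period 2 |

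Visits 3, 15 and 27 disagree. Across three sequences that makes 9 sequence-by-visit cells, and the period changes in all 9.

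**Where the treatment also changes.**
- Sequence 1, Visit 3: Run-In placebo is counted as rozanolixizumab 12 weeks.
- Sequence 2, Visit 15: placebo is counted as rozanolixizumab 12 weeks.
- Sequence 1, Visit 15: rozanolixizumab 12 weeks is counted as the 12-to-24-week group.
- Sequences 1 and 2, Visit 27: the sample leaves Period 2 for Run-Out. Table 5-3 has no Run-Out group, so the label depends on the table layout.
- Sequence 2 at Visit 3, and Sequence 3 at all three visits: only the period changes.

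So 3 of 9 cells change treatment group, 2 depend on layout, and 4 change period only. If 5.6.9.5 used the adverse-event columns of SAP 5.6.2 instead of Table 5-3, the first two cells would still sit under rozanolixizumab (RLZ in Period 1, PBO/RLZ in Period 2).

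**Samples by treatment group, 20 per sequence, no dropout.**
- Rozanolixizumab 12 weeks, by day range: Sequence 1 Visits 3, 7, 11 (3 × 20 = 60) plus Sequence 2 Visits 15, 19, 23 (60) = 120. Before any rozanolixizumab: 20 + 20 = 40, and 40/120 = 33%.
- Rozanolixizumab 24 weeks, by day range: Sequence 1 Visits 15, 19, 23 = 60. Reflecting only the first 12 weeks: 20, and 20/60 = 33%.
- Visit 27 samples of Sequences 1 and 2 moved to Run-Out: 20 + 20 = 40.

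With the visit rule extended, Period 1 holds Visits 7, 11 and 15, Period 2 holds Visits 19, 23 and 27, and all three counts of misplaced samples are 0.

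**Windows.** Visits may move by 2 days. A Visit 15 held on Day 84 would be Period 1 by the day range but Period 2 by first-dose date. The two general rules can therefore disagree with each other, and a visit rule avoids this.

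**The case against.** The strongest reply is that silence is not a rule. Nothing in the SAP tells a programmer to allocate laboratory samples by date: Appendix 4 does not mention them, the day-range tables are descriptive, and the TFL shells, which are separate documents, may settle the matter. This stands in part. A reader might infer that the SAP prescribes the wrong allocation, and it does not. The text does leave the general definitions as the only guide, and a prespecified liver table should not depend on a guess.

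A reader might also infer that laboratory and vital-sign tables are wrong throughout. They are not. SAP 5.6.6 and 5.6.7 present results by sequence with visit or time point, so a Visit 15 value in Sequence 2 stays recognisable whatever period heading it carries.

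It is tempting to say that Visit 27 elevations lose their active label, so that treatment is misattributed in both directions. The documents show only a change of period. The adverse-event layout keeps the sequence labels through Run-Out and follow-up, and Protocol 9.4.1 tabulates follow-up events of Sequences 1 and 2 under active treatment.

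Cases can be recovered by hand. SAP 5.6.9.5 lists all results for participants meeting the combined transaminase and bilirubin criteria, 5.6.4 lists Potential Hy's Law with the most recent treatment, and 5.6.6 lists every chemistry value by sequence and time point. That limits the harm in a trial of about 60, but it does not make the summary table correct.

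Finally, the Visit 3 and Visit 15 placements count against rozanolixizumab, and same-day adverse events already go to the new period, so the effect could be called conservative. The SAP states no such intent for laboratory data, and moving Visit 27 takes the sample that follows all 12 doses out of Period 2.

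**Conclusion.** The point holds as a gap with a specific consequence. No explicit period rule covers safety laboratory data, and the general definitions would place pre-dose samples at Visits 3, 15 and 27 in the following period. The consequence is confined to the pDILI, Hy's Law and liver function summaries in SAP 5.6.9.5. There, elevations at Visit 3 in Sequence 1 and Visit 15 in Sequence 2 would be counted as rozanolixizumab before any was given. Visit 15 in Sequence 1 would count as extended exposure. Visit 27 carries a period error, with the treatment label depending on layout.

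The size, one third of scheduled samples in each rozanolixizumab group, assumes 20 per sequence, no dropout, nominal visit days and allocation by the general definitions. It counts samples. The documents give no rate of liver events, so it should not be read as one third of events, nor as wrong treatment for all 60 participants. Exclusion criterion 28 bars ALT, AST or ALP above twice the upper limit of normal, so a threefold ALT or AST result at Visit 3 would generally need a new rise, and the number of affected cases may be small. A change is worth making because the table could otherwise be wrong and the correction is minor.

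**What to change.** For the 5.6.9.5 summaries, add one sentence to SAP 5.1.1.2 extending the visit rule to safety laboratory data: pre-dose Visit 3 to Run-In, pre-dose Visit 15 to Treatment Period 1, and pre-dose Visit 27 to Treatment Period 2. State in 5.6.9.5 that this rule governs the period and treatment group of each result, and how Run-Out results are labelled. The tables in 5.6.6 and 5.6.7 need no change of substance.

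The cost is the added text and one change to the period derivation, with no new data. It is best made before the unblinding for the Early Readout Analysis.

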#### **5.1.1.3        Definition of Baseline Values**

Endpoint-specific Baseline definitions are presented in [Table 5-2](#). Scheduled or unscheduled measurements may be used as the Baseline value. If a measurement is missing or repeated at Baseline, and is obtained prior to the first dose of IMP in the Run-In Period/at Day 1 (dependent upon the endpoint), then the last available measurement will be used as the Baseline value. In rare circumstances the latest observation may be a data point collected at an unscheduled visit - such an observation would also be allowable as Baseline value.

**Table 5-2: Definition of Baseline**

Endpoint	Definition of Baseline
Hematology, serum chemistry, urinalysis, vital signs	Baseline is defined as the most recent value obtained prior to the first dose of IMP in the Run-In Period, or Screening if this is missing.
Efficacy	
Baseline is defined as the measurements on Day 1 (Visit 3, Week 1) prior to administration of treatment or during Run-In Period depending on the endpoint:
 
 
For BPI-SF, the Baseline measurement is at Day 1 (Visit 3, Week 1). If Day 1 measurement is missing, then the Screening measurement will be used.
 
For Pain NRS, and Fatigue NRS, the Baseline measurement will be the average of the 7 days prior to Day 1 (Visit 3, Week 1), not including Day 1 data. If there are <3 assessments available within the 7 days, the Baseline measurement will be missing.
 
For FIQR, the Baseline will be the last assessment before Day 1. This is Day -7 (Visit 2, Week -1) or Screening visit if Day-7 is missing.
 
 
Note that for all endpoints listed above, if a dose of study medication was not received at Visit 3, but the efficacy assessment was performed at Visit 3 (or Visit 2 for FIQR), the Baseline assessment would be defined as above.

Pharmacodynamics (PD)	
Baseline is defined as the latest non-missing assessment performed prior to dosing on Day 1 (Visit 3, Week 1). If Day 1 measurement is missing, the Run-In (Visit 1, Week -2) measurement will be used.
 
Note that if a dose of study medication was not received at Visit 3, but the PD assessment was performed at Visit 3, this would still be used as the Baseline assessment.

Pressure Pain Threshold	
Baseline is defined as the average of the three assessments performed per site, prior to dosing on Day 1 (Visit 3, Week 1).
 
Note that if a dose of study medication was not received at Visit 3, but the Pressure Pain Threshold assessment was performed at Visit 3, this assessment would still be used as the Baseline assessment.

Anti-drug antibody (ADA)	
Baseline is defined as the last measurement prior to receiving the first dose of rozanolixizumab. For participants randomized to Sequence 1, Baseline is the Day 1 (Visit 3, Week 1) pre-dose assessment, or Day -7 (Visit 1, Week -1), if missing. For participants randomized to Sequence 2, Baseline is the Day 85 (Visit 15, Week 13) pre-dose assessment, or Day 1 (Week 3, Visit 1), if missing.
 
Note that if a dose of study medication was not received at Visit 3, or Visit 15 (dependent upon the participant), but the ADA assessment was performed at Visit 3 or Visit 15, this assessment would still be used as the Baseline assessment.

